1. OVERVIEW

The purpose of the Statistical Analysis Plan (SAP) is to ensure the credibility of the study results by pre-specifying the statistical approaches for the analysis of study data prior to database lock. The SAP is intended to be a comprehensive and detailed description of the definitions and statistical methods to be used in the analysis of data for study R475-PN-1523.

This plan may be revised during the study to accommodate protocol amendments and/or to make changes to adapt to unexpected issues in study execution and/or data that affect planned analyses. These revisions will be based on blinded review of the study and data, and a final plan will be issued prior to the first step database lock and before unblinding of the study.

1.1. Background/Rationale

This is a Phase 3, randomized, double-blind, placebo-controlled study designed to evaluate the long-term safety, tolerability, and the efficacy of fasinumab in patients with pain due to radiographically confirmed OA of the knee or hip who have a history of inadequate pain relief with paracetamol/acetaminophen, and a history of inadequate pain relief or intolerance to oral NSAIDs, and opioid therapy. During the initial 16 weeks of the trial, standard-of-care pain medications will be prohibited with the exception of paracetamol/acetaminophen, which will be provided as a rescue medication, and low-dose aspirin for cardiac prophylaxis. Following the first 16 weeks, patients will be able to utilize standard-of-care pain medication including limited use NSAIDs (for non-OA pain or fever), as well as paracetamol/acetaminophen, in addition to study drug. Therefore, this study will also provide safety data on the concomitant use of fasinumab with other analgesics, including limited use NSAIDs.

A subset of patients will participate in an efficacy sub-study, in addition to participation in the main long-term safety study. In the sub-study, efficacy parameters will be assessed over the 16 weeks following randomization to a treatment group. Details on dosing regimen and allocation ratios across amendments for both the main study and efficacy sub-study are provided in Section 2.1.

There have been several modifications to the dosing regimens for the study. Patients initially randomized to the 6 mg or 9 mg Q4W dosing regimen or matching placebo under the original protocol and amendments 1 and 2 were discontinued from study medication on 30December 2016 per US FDA request. The patients were encouraged to otherwise continue all protocol visits and complete all study procedures with the exception of receiving study medication. Under amendments 3 and 4, main study patients were randomized to 6 mg Q8W or matching placebo. Under amendment 5 global (Issued 16March 2017) or later amendments, main study patients were randomized to 6 mg fasinumab Q8W, 3 mg fasinumab Q4W, 1 mg Fasinumab Q4W, or matching placebo. Efficacy sub-study patients were randomized to 6 mg fasinumab Q8W, 3 mg fasinumab Q4W, 1 mg fasinumab Q4W, 1 mg fasinumab Q8W, or matching placebo Q4W. Patients randomized to efficacy sub-study will continue in the main study on randomized treatment after participation in the efficacy sub-study. Prior to amendment 5 global all subjects participated only in the main study. Enrollment for the main study under

amendment 5 or later was paused on 3 January 2017 not due to any safety concern, but to hold enrollment of 6 mg Q8W vs placebo until further discussion with health authorities on safety database requirement. The efficacy sub-study has completed enrollment as of 7 February 2018.

The Data Monitoring Committee recommended that the 3mg Q4W and 6mg Q8W doses be discontinued due to safety concerns. A decision was made by the Sponsor to conduct an unplanned interim safety analysis of the data to corroborate these findings. Based on the IDMC recommendation and the totality of evidence to date with regards to safety, only the 1mg Q4W, 1mg Q8W doses and placebo arms would be carried forward in the study. The 3 mg Q4W and 6Mg Q8W doses were discontinued from further dosing; however, subjects have been encouraged to remain in the study and will be followed for all study visits until completion of the end of study visit in order to continue to monitor for safety and to allow complete data collection.

The Abridged Unblinded DMC Interim Report was made available to members of the study team including the study biostatistician and study medical director. This abridged DMC report included the following subject level listings:

- Listing of Serious of Adverse Events from the Case Report Form (amendment 3)
- Listing of Serious of Adverse Events from the Case Report Form (amendment 5 sub-study)
- Listing of Deaths (amendment 3)
- Listing of Adjudication Results for Subjects with Arthropathies (amendment 3)
- Listing of Adjudication Results for Subjects with Arthropathies (amendment 5 Sub-study), Listing of Subjects with Total Joint Replacement (amendment 3)
- Listing of Subjects with Total Joint Replacement (amendment 5 Sub-study)

Restricted to subjects randomized to Placebo SC Q4W or Q8W (amendments 3 or earlier), 6 mg SC Q4W or Q8W (amendments 3 or earlier), Placebo SC Q4W (amendment 5 sub-study), 3 mg SC Q4W (amendment 5 sub-study), 6 mg SC Q8W (amendment 5 sub-study). This report did not contain any information on the 1mg Q4W and 1mg Q8W doses or their placebo arms that are being carried forward; hence there is no risk of unblinding of the blinded study team members to doses being continued. Continued monitoring of all subjects not being dosed also remains blinded to the clinical team as to treatment received.

Given the discontinuation of the 3 mg and 6 mg doses, greater exposure to the fasinumab 1 mg dose was required to increase the size of the fasinumab safety database for potentially clinically relevant doses. Therefore, under amendment 8, patients will be randomized in a 3:3:1 ratio to fasinumab 1 mg Q8W, 1 mg Q4W or placebo. This randomization ratio was chosen based on the need to enroll more patients on the 1 mg dose regimens and the need to include placebo patients for blinding purposes.

Supportive trials include data from 2 completed fasinumab phase 1 studies in healthy volunteers (R475-PN-0817 and TD-11480), as well as data from the completed fasinumab phase 2 proof-of-concept study in patients with pain due to OA of the knee (R475-PN-0901), and results from the phase 2 study in patients with osteoarthritis of the hip or knee (R475-PN-1227).

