**Amendment 7**

The primary purpose of this amendment is to incorporate an urgent safety measure, which requires discontinuing the 3 mg every 4 weeks (Q4W) and 6 mg every 8 weeks (Q8W) dose regimens. The recommendation by the independent Data Monitoring Committee (DMC) to discontinue these dose regimens was made following a review of unblinded data from this ongoing study and was based on an imbalance in clinically relevant adverse events including time to total joint replacement, peripheral edema, arthralgia and a trend towards early fractures in the 6 mg Q8W group. Based on the independent DMC review, study of lower dose levels (eg, 1 mg Q4W) may continue to be evaluated in this population. With this amendment, patients randomized to the 3 mg Q4W or 6 mg Q8W dose regimens will be permanently discontinued from study drug but encouraged to otherwise complete all remaining study visits and study procedures in the follow up period and the end of study phone call.

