### 1.3.2. Rationale for Dose Selection

Previous versions of this protocol randomized patients to receive fixed-dose, subcutaneous (SC) injections of fasinumab at 6 mg Q8W (amendment 3 onwards in the main study) and 1 mg Q8W, 1 mg Q4W, 3 mg Q4W, 6 mg Q8W (amendment 5 in the efficacy sub-study), or matching placebo. The purpose of the 1 mg Q8W dose regimen is to aid in the determination of a minimally effective dose. An independent DMC recommended discontinuing 6 mg Q8W and 3 mg Q4W (expected to have similar exposure to 6 mg Q8W) following a review of unblinded data from this ongoing study. The recommendation was based on an imbalance in clinically relevant adverse events including time to total joint replacement, peripheral edema, arthralgia and a trend towards early fractures in patients administered 6 mg Q4W (dose discontinued in amendment 3, issued on 20 June 2016) or 6 mg Q8W. Based on the independent DMC review, study of lower dose levels (eg, 1 mg Q4W) may continue to be evaluated in this population. Under amendment 7, issued on 24 May 2018, all patients previously randomized to 3 mg Q4W or 6 mg Q8W under earlier versions of the protocol were discontinued from study drug but encouraged to complete all remaining study visits and study procedures in the follow-up period, and the end of study phone call. Given the discontinuation of the 3 mg and 6 mg doses, greater exposure to the fasinumab 1 mg dose is required to increase the size of the fasinumab safety database for potentially clinically relevant doses. Under amendment 8, issued on 11 Jul 2018, patients will be in a 3:3:1 ratio to fasinumab 1 mg Q8W, 1 mg Q4W or placebo. This randomization ratio was chosen based on the need to enroll more patients on the 1 mg dose regimens and the need to include placebo patients for blinding purposes.

Patients originally randomized to 6 mg Q4W or 9 mg Q4W were transitioned to 6 mg Q8W in amendment 3 (issued on 20 June 2016). These patients and patients on matching placebo were subsequently discontinued from study drug in amendment R475-PN-1523.04EU (issued on 12 January 2017) and amendment 5 global (issued on 16 March 2017), but encouraged to otherwise continue all protocol visits and complete all study procedures with the exception of receiving study drug. This decision was based on data from the phase 2/3 study, R475-PN-1227, which showed an increase in AA events that occurred more frequently at the highest doses evaluated (6 mg and 9 mg Q4W).

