## 5. STUDY TREATMENTS

### 5.1. Investigational and Reference Treatments

Under amendment 8 and amendment 9, patients will be enrolled into the main safety study and randomized to 1 of the following treatment arms:

- Fasinumab 1 mg SC Q8W (patients will receive placebo injections at the study visits where fasinumab is not administered)
- Fasinumab 1 mg SC Q4W
- Placebo SC Q4W

Prior to amendment 7 (urgent safety measure), patients were randomized to 6 mg Q8W or placebo in the main study (after amendment 3), and to the following treatment arms in the efficacy sub-study (amendment 5):

- Fasinumab 1 mg SC Q8W (included in the efficacy sub-study only; patients will receive placebo injections at the study visits where fasinumab is not administered)
- Fasinumab 1 mg SC Q4W
- Fasinumab 3 mg SC Q4W
- Fasinumab 6 mg SC Q8W (patients will receive placebo injections at the study visits where fasinumab is not administered)
- Placebo SC Q4W

Enrollment into the efficacy sub-study was completed prior to amendment 7.

All patients previously enrolled into the main study had completed treatment prior to amendment 7. Under amendment 7, patients randomized to 3 mg Q4W or 6 mg Q8W in the efficacy sub-study were discontinued from study drug for the remainder of the study. All patients who were discontinued from study drug immediately entered the follow-up period.

Patients originally randomized to earlier versions of the protocol (prior to amendment 3) with 9 mg Q4W, 6 mg Q4W, or placebo Q4W were discontinued from study drug for the remainder of the study under an amendment 4EU (issued on 12 January 2017) and amendment 5 global (issued on 16 March 2017).

All patients will receive SC injections Q4W from day 1 up to week 48. All SC injections will be in the abdomen, thigh, or upper arm. Study drug (fasinumab or placebo) will be administered at the study site after all study visit procedures have been completed. Patients will be observed in the clinic for approximately 1 hour after study drug is administered.

Instructions for study drug administration are provided in the pharmacy manual.

Doses of study drug must be given within  $\pm 7$  days from the scheduled dose date. If the window is missed, the dose should not be administered. The next dose should be administered at the next scheduled dosing date.

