##### **5.3.2.1. Reasons for Permanent Discontinuation of Study Drug**

Study drug dosing will be permanently stopped in the event of:

- A patient being randomized under amendment 3 or a subsequent amendment and treated with the 3 mg Q4W or 6 mg Q8W dosing regimen
- A patient being randomized under an earlier version of the protocol before amendment 3 and treated with the 6 mg Q4W, 9 mg Q4W, or placebo Q4W dosing regimen
- A subject developing clinically significant sensory and motor neurologic events confirmed by a neurologist's examination and graded by the neurologist as at least

moderate peripheral neuropathy limiting activities of daily living, ie, grade  $\geq 2$  according to v.4 (CTCAE); study sites should use CTCAE v.4 criteria throughout the study for consistency

- Evidence of pregnancy
- A patient developing new or worsening signs and symptoms indicative of carpal tunnel syndrome
- Continued noncompliance with protocol-defined maximum NSAID use (see Section 4.3) after appropriate counseling
- Continued noncompliance with protocol-defined maximum acetaminophen/paracetamol use (with a maximum daily dose of 2500 mg in Europe and other countries where 500 mg strength tablets/capsules are available and 2600 mg in any countries outside of Europe where 325 mg strength tablets/capsules are available) after appropriate counseling
- JR Surgery
- AESI:
  - Adjudicated arthropathy, as described in Section 7.6.1.1
  - Sympathetic nervous system dysfunction, as described in Section 7.6.1.2
- Hepatotoxicity
  - Study drug should be discontinued if:
    - a) Total bilirubin (TBL)  $>2x$  ULN or international normalized ratio (INR)  $>1.5$  and
    - b) Alanine aminotransferase (ALT) or aspartate aminotransferase (AST)  $>3x$  ULN and
    - c) No other cause for a and b is readily apparent

Other causes of ALT, AST, and TBL elevations can include alcoholic hepatitis, autoimmune hepatitis, non-alcoholic hepatitis, heritable diseases (Gilbert's Syndrome), heart failure, and viral hepatitis.

Study drug may be withheld in patients who do not meet criteria for permanently discontinuing study drug, until an alternative cause for drug-induced liver injury can be determined. The patient may be re-challenged if an alternative cause for elevated liver function tests is found and the liver function tests return to baseline, but only after discussion with the sponsor.

- Systemic hypersensitivity reaction assessed as related to study medication

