### 5.5.1. Blinding

Study patients, the principal investigators, and study site personnel will remain blinded to all randomization assignments throughout the study. The Regeneron study medical director, study monitor, and any other Regeneron and contract research organization (CRO) personnel who are in regular contact with the study site will remain blinded to all patient randomization assignments.

Blinded study drug kits coded with a medication numbering system will be used. In order to maintain the blind, lists linking these codes with product lot numbers will not be accessible to individuals involved in study conduct.

Anti-drug antibody (ADA) results will not be communicated to the sites before the end of the study, and the sponsor operational team will not have access to results associated with patient identification until after the final database lock.

No study personnel involved in the day-to-day conduct of the study will have access to unblinded data before the database is locked for this study.

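### Being stopped under Amendment 7 reveals active treatment, so three blinding statements need qualifying and analyses that run past the stop need a supportive split

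*SAP*

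**What the plan says.** **The stop.** Protocol 5.1: "Under amendment 7, patients randomized to 3 mg Q4W or 6 mg Q8W in the efficacy sub-study were discontinued from study drug". The standing rule in Protocol 5.3.2.1 for patients randomized under amendment 3 or later covers those "treated with the 3 mg Q4W or 6 mg Q8W dosing regimen"; placebo is not listed. SAP 1.1 confirms that "only the 1mg Q4W, 1mg Q8W doses and placebo arms would be carried forward in the study", and Protocol 3.1 keeps placebo injections going in treatment period 2. Protocol 3.1 and 5.1 move the stopped patients into follow-up at once.

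**The earlier stop was different.** For patients randomized before amendment 3, Protocol 5.3.2.1 covers those "treated with the 6 mg Q4W, 9 mg Q4W, or placebo Q4W dosing regimen". Protocol 1.3.2 agrees: "These patients and patients on matching placebo were subsequently discontinued from study drug".

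**Blinding.** SAP 1.1 says: "Continued monitoring of all subjects not being dosed also remains blinded to the clinical team as to treatment received". Protocol 5.5.1 says: "Study patients, the principal investigators, and study site personnel will remain blinded to all randomization assignments throughout the study". Protocol 7.5.2 describes the investigator who rates causality as blinded.

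**Analysis.** The safety set in SAP 3.2 keeps every randomized and dosed patient. SAP 5.1.7.1 fits a Poisson rate model with log observation days as the offset, and SAP 5.1.6.3 runs observation to the end-of-follow-up clinic visit. SAP 5.1.8 compares time to JR decision with placebo by Cox regression. SAP 4.5.1 makes JR incidence, including the telephone survey, a primary safety variable. SAP 5.1.8.1 tabulates treatment-emergent, post-treatment and whole-study adverse events. None of these is split at the Amendment 7 stop.

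**The concern.** A stop confined to active arms identifies active treatment, and everyone can see it: injections cease and the visit schedule changes. Protocol 1.1 and 1.3.2 also name the two withdrawn regimens and the reasons (joint replacement, peripheral edema, arthralgia, a trend to early fractures). Protocol 13.2 requires that patients be told of new safety information that significantly changes the risk/benefit assessment.

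Several outcomes depend on judgment: reporting of joint pain, imaging triggered by the investigator's view of that pain, the decision to replace a joint, whether a JR counts as an event of special interest (Protocol 7.6.1.4), and the causality rating. After the stop, these judgments are made in the two arms with active treatment inferable and an alarm known, while placebo patients remain on injections with their assignment hidden. The likely direction of any bias is upward in the stopped arms, and in combined fasinumab if they belong to it. The primary objective is to describe safety, so the report should say which follow-up was blinded and which was not.

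**Working it through.** The blinding claim has no stated figure to reproduce. The nearest one fixes the arm size.

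**1. Arm size.** Inputs (SAP 2.2, Protocol 9.2): 200 per arm, 15% dropout, two-sided level 0.0167. Evaluable n = 200 × 0.85 = 170. Power = Φ(δ√(n/2) − z), with √85 = 9.22 and z = 2.393.
- δ = 0.46: Φ(4.241 − 2.393) = 96.8% (stated: at least 96%).
- δ = 0.36: Φ(3.319 − 2.393) = 82.3% (stated: at least 82%).

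Five arms × 200 = 1000, the stated sub-study size.

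**2. What the stop reveals.** Sub-study allocation is 1:1:1:1:1 (SAP 2.1).
- P(active) at randomization = 4/5 = 80%.
- P(active | stopped by Amendment 7) = 2/(2 + 0) = 100%.
- P(3 mg | stopped by Amendment 7) = 1/2, so the regimen stays hidden.
- P(placebo | carried forward) = 1/3 = 33%, against 20% at randomization; no individual assignment is revealed.
- Contrast, before amendment 3 (2:2:1, placebo also stopped): 4/5 = 80% both before and after.

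**3. If an observer could not tell this stop from an individual one.** Suppose a share b of each carried-forward arm is off drug for individual reasons (assumption). Then P(active | off drug) = (2 + 2b)/(2 + 3b). With b = 5%: 2.10/2.15 = 97.7%. With b = 30%: 2.60/2.90 = 89.7%.

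**4. How many patients.** Planned ceiling: 2 × 200 = 400. Protocol 5.1 says main-study patients had already completed treatment. The number of sub-study patients still on drug is not given. If enrollment was even from 16 March 2017 to 7 February 2018 (assumption; 328 days), those randomized within 48 weeks (336 days) of 24 May 2018 entered in the last 230 days: 230/328 = 70%, or about 280 of 400 before individual discontinuations. The possible range is 0 to 400.

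**5. How long.** From 7 February to 24 May 2018 is 106 days, or 15.1 weeks. For a patient randomized on the last enrollment date, with last dose at week 12:

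| Window | Ends at week | Weeks after 24 May 2018 |
|---|---|---|
| Treatment-emergent (last dose + 4) | 16 | 0.9 |
| Clinic follow-up (last dose + 24) | 36 | 20.9 |
| Telephone contact (last dose + 52) | 64 | 48.9 |

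This patient has a high share of post-stop time: 20.9/36 = 58%. In general, a last dose 0 to 4 weeks before the stop leaves 20 to 24 clinic weeks after it. For a last dose at week 44, follow-up ends at week 68, so the share is 20/68 to 24/68, or 29% to 35%.

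**6. Which analyses this reaches.** The treatment-emergent window holds at most about 4 post-stop weeks. Observation-period rates and whole-study tables hold 20 to 24. JR by telephone reaches further still.

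**The case against.** The best defence has five parts.

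- **The SAP sentence is narrower than it looks.** It concerns the clinical team, in a paragraph about who saw the abridged monitoring report. It also covers patients stopped before amendment 3 and main-study completers, for whom being undosed reveals nothing. This stands for those two groups. It does not rescue the sentence for Amendment 7 patients: dosing status is in the study data, and SAP 1.1 records that the medical director and biostatistician had subject-level listings covering these arms. Protocol 5.5.1 speaks of patients and sites directly.
- **Later events are not simply pooled.** A reader might infer that the SAP mixes all post-stop events into its main safety results. It does not: treatment-emergent events end 28 days after last dose, later events form a separate class, and SAP 5.1.8.1 puts the reporting focus on the former. What remains is the set of analyses without a split.
- **Arthropathy is protected.** An independent blinded committee adjudicates it (Protocol 3.4), and radiographs are scheduled for everyone at weeks 24 and 52 and at 12 and 24 weeks after last dose. This stands; referral for extra imaging is the only open route.
- **Combined fasinumab may not include these arms.** SAP 2.1 says the plan now includes only the 1 mg doses and placebo, whereas the SAP 3.2 safety set includes all dosed patients. The text does not settle it.
- **Censoring has a price.** Long follow-up exists to catch delayed joint harm. A headline result censored at the stop would move that harm out of view in the higher-dose arms and give unequal follow-up in a constant-rate model. This is a good reason not to replace the planned analysis.

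**Conclusion.** The concern holds in limited form. For patients stopped under Amendment 7, the blinding claims in SAP 1.1, Protocol 5.5.1 and Protocol 7.5.2 are untrue from the stop onward: active treatment is certain, although 3 mg and 6 mg remain indistinguishable. The exposed results are the observation-period incidence rates, whole-study adverse event tables, JR incidence and time to JR decision in those two arms.

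Two further inferences are tempting but unsupported. One is that the 1 mg versus placebo comparison is compromised; patients in those arms kept their injections, and their individual assignments are not revealed by the amendment. The other is that about 400 patients are affected; that is a planned ceiling.

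The size of any bias cannot be computed from the documents. The week counts assume that the stop date equals the issue date of 24 May 2018 and that the last patient was randomized on 7 February 2018; the documents do not say when sites acted. The enrollment calculation follows SAP 1.1 in taking sub-study enrollment to begin under amendment 5. SAP 2.1 can be read as having some earlier, but the 100% result does not depend on this.

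**What to change.** 1. Qualify SAP 1.1, Protocol 5.5.1 and Protocol 7.5.2: for patients stopped under Amendment 7, active treatment can be inferred from the stop date, though not which of the two regimens. Leave the statements in place for patients stopped before amendment 3 and for main-study completers.
2. Reconcile SAP 2.1 with SAP 3.2 and state whether combined fasinumab includes the discontinued regimens.
3. Keep the uncensored analysis as planned. In SAP 5.1.7.1, 5.1.8 and 5.1.8.1, add a supportive analysis of incidence rates, JR and time to JR decision for the 3 mg Q4W and 6 mg Q8W arms (and combined fasinumab if they are included), censored at or split by the Amendment 7 stop date. Label post-stop events, including those in whole-study tables, as known-treatment follow-up.
4. Define the stop date. The SAP refers to the last-dose date and the reason for discontinuation but not to a date of stop under this amendment, so a derivation rule is needed.

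The cost is SAP and protocol wording, one derived date and a few extra tables. The supportive blinded-period rates will have less person-time. No events are lost, because the planned analysis stays.
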